1.5.2 Objectives

Trial objectives are:

- a) To investigate the effects of a six-week remote multicomponent rehabilitation intervention compared to standard care on physical function, illness perceptions, fatigue, anxiety, depression, and adverse events at eight weeks post-randomisation.
- b) To investigate longer term effects of a six-week remote multicomponent rehabilitation programme compared to standard care on health-related quality of life, physical function, illness perceptions, fatigue, anxiety, and depression at six months post-randomisation.
- c) To determine explanatory factors influencing outcomes via an embedded process evaluation.
- d) To evaluate the cost-effectiveness of the multicomponent rehabilitation intervention compared to standard care over six months follow-up.

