5. ADVERSE EVENT MANAGEMENT

5.1 Definitions

5.1.1 Adverse Events (AE)

An Adverse Event (AE) is defined as any untoward medical occurrence in a clinical trial participant which does not necessarily have a causal relationship with the treatment/intervention.

AEs exempt from recording

These are common AEs associated with exercise and will not be recorded as AEs for this trial (Table 4)

Table 4 – Common AEs associated with exercise

Events
Breathlessness
Light headedness/dizziness
Muscle stiffness/soreness
Tiredness/fatigue
Oxygen desaturation (that resolves with appropriate management e.g. rest, breathing exercises, inhaled medications)

For the **intervention group**, AEs listed in Table 4 that are identified during or after the intervention, will be recorded on the intervention notes (not on an AE form), for clinical purposes only. For all participants, AEs listed in Table 4 identified during outcome assessment will be recorded on the iRehab database.

Any AEs that are not listed in Table 4 should be recorded using the Adverse Event eCRF. Recording should be done by the intervention team, outcome assessor or investigator site, as appropriate, within 48 hours of becoming aware of the AE. All AEs should be assessed to see if they constitute a 'Serious' adverse event as per section 5.1.2 below. If they do, they will be reported by the mechanism in section 5 and not recorded on the AE form.

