5.2 Assessing and Reporting AEs, SAEs and related SAEs

5.2.1 Recording and assessing AEs/SAEs

All **AEs** and **SAEs** (unless otherwise specified) occurring from the time of **informed consent** until 8 weeks post randomisation and during the 8 week and 6-month outcome assessment appointments, must be recorded (AE)/reported (SAE) (where events are usually within 48 hours of the assessment appointment).

During the baseline, eight- week or six-month assessment all participants will be asked about anything that might constitute an AE or SAE by the independent assessor performing the assessment. AEs/SAEs occurring during the intervention delivery in the intervention group will be determined through patient report at each weekly online catch-up session.

All SAEs, except for those listed in Table 5, should be initially reported by the site, the outcome assessor or a member of the intervention delivery team, as appropriate. A copy of the SAE form should be sent to the WCTU trial team via the trial database and the WCTU QA Team will be notified by the WCTU trial team. WCTU should be informed **within 24 hours** of any party becoming aware of the event.

Once received, the trial management team at WCTU will review the SAE. Information will be requested from the recruiting site to provide further detail on the SAE if required. If the patient was treated for the SAE at the investigator site that recruited the patient, WCTU will send the SAE on to the investigator site for completion within 2 working days (if not already reported by the site). If not then WCTU will contact the patient or the patients GP for further information where applicable.

For each **SAE** the following information will be collected from the intervention team, assessor and/or investigator site (as appropriate):

- details in medical terms and case description
- event duration (start and end dates, if applicable)
- action taken
- outcome

- seriousness criteria
- causality (i.e. relatedness to intervention), in the opinion of the investigator

The causality of SAEs (i.e. relationship to trial treatment) will be assessed by the site Principal Investigator and Chief Investigator(s) on the SAE form using Table 6.

Table 6 – SAE causal relationships

Relationship to trial intervention	Description
Unrelated	There is no evidence of any causal relationship

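### Up to seven active adverse-event enquiries in the intervention arm against one in control by week 8 are likely to over-count non-serious AEs and patient-reported SAEs in the intervention arm

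*Protocol*

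**What the plan says.** Objective (a) in Protocol section 1.5.2 is to study the intervention "compared to standard care on physical function, illness perceptions, fatigue, anxiety, depression, and adverse events at eight weeks post-randomisation". Adverse events are thus a stated between-arm comparison.

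Section 5.2.1 sets how events are found. At baseline, week 8 and month 6, "all participants will be asked about anything that might constitute an AE or SAE by the independent assessor". The next sentence applies to one arm only: "AEs/SAEs occurring during the intervention delivery in the intervention group will be determined through patient report at each weekly online catch-up session". The recording window runs from consent to week 8 after randomisation, plus the week-8 and month-6 appointments, with the qualifier "where events are usually within 48 hours of the assessment appointment".

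Section 5.1.1 sends AEs from three kinds of reporter to the same form: "Recording should be done by the intervention team, outcome assessor or investigator site, as appropriate, within 48 hours of becoming aware of the AE". It treats the common exercise-related events in Table 4 differently. When found during or after the intervention they stay in the intervention notes; when found at outcome assessment they go on the trial database for all participants.

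Sites report all readmissions (5.5), and all deaths are reported (5.6). Under 2.7.1 control participants receive usual NHS care only. Under 2.9 the assessor should not know the allocation. The delivery team necessarily does, since it is notified only of intervention participants (2.6.1).

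**The concern.** The number of events recorded in an arm depends on how many occur and on how hard one looks. Here the protocol looks harder in one arm, inside the main harms window, through staff who know the allocation and see no control participants. With equal true rates, the intervention arm would be expected to show more recorded events of any kind that comes to light mainly by asking.

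Two errors could follow. The intervention could appear less safe than it is, in the final report or in the unblinded safety data that the DMC reviews for patterns (5.4, 8.10). Or a real excess could be put down to the extra questioning, with no way to tell the two apart. The primary outcome is not affected.

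**Working it through.** There is no stated figure to reproduce. The check is a count of enquiries, a sort of event types by route, and an illustration on assumed detection rates.

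**1. Active enquiries from randomisation to week 8**

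| Source | Intervention | Control |
|---|---|---|
| Weekly session (Table 1, 5.2.1) | up to 6 | 0 |
| Assessor at week 8 (5.2.1) | 1 | 1 |
| Total | up to 7 | 1 |

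It is up to seven because sessions may be missed or start late (2.7.2 allows up to three weeks to first contact). Table 3 ticks AEs and SAEs under weeks 1-6 without naming an arm, but no section describes a control-arm enquiry in those weeks.

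**2. Which events are exposed**

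- Deaths: reported irrespective of cause, with no arm restriction (5.6). Largely protected.
- Readmissions: reported by sites for all participants (5.5). Largely protected.
- Table 4 events: session reports stay off the AE form, and assessor reports are recorded in both arms (5.1.1). Largely protected.
- Non-serious AEs outside Table 4: up to seven enquiries against one, plus whatever sites happen to learn. Exposed.
- SAEs known only by patient report, without admission or death: exposed in the same way.

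**3. Size, on assumed detection rates**

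Let the true risk be p in both arms, and the detection probabilities d_I and d_C. The expected recorded risk ratio is (p × d_I)/(p × d_C) = d_I/d_C, so p cancels. The protocol gives neither d_I nor d_C; 0.90 and 0.50-0.70 are assumptions.

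- d_C = 0.70: 0.90/0.70 = 1.29
- d_C = 0.50: 0.90/0.50 = 1.80
- d_C = 0.90 (equal enquiry): 0.90/0.90 = 1.00

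For example, at p = 20% the expected recorded risk is 0.20 × 0.90 = 18% in the intervention arm, against 0.20 × 0.70 = 14% or 0.20 × 0.50 = 10% in control.

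To see how convincing such a gap could look, take the planned 231 and 197 participants, no losses, and a two-sided 5% comparison of proportions. The protocol specifies no such test. The chance of a falsely significant excess in the intervention arm is then:

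| True risk | d_C = 0.70 | d_C = 0.50 | d_C = 0.90 |
|---|---|---|---|
| 10% | 11% | 36% | 2.5% |
| 20% | 20% | 66% | 2.5% |
| 40% | 42% | 96% | 2.5% |

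**4. The 48-hour wording**

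The qualifier in 5.2.1 can be read in two ways.

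- If it describes only events provoked by the appointment itself, the week-8 enquiry is open-ended and control events rest on recall over eight weeks.
- If it describes the look-back, the control arm's single enquiry covers about 2 of 56 days (2/56 = 3.6%), and the assessor's enquiry alone would miss most of weeks 1-6 in both arms.

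The section does not settle which is meant, and any comparison built on the assessor's enquiry depends on it.

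**The case against.** The strongest reply is that the protocol already limits the damage. For the exercise-related events it expects to be common, it keeps session reports off the AE form and uses the assessor's record in both arms, which is the principle argued for here. Control events can also arrive without an enquiry: sites may record AEs and report SAEs, readmissions and deaths, exempt SAEs are captured in questionnaires or the readmission form (5.1.2), and a helpline is open to all participants (2.6.4). The listed safety outcome is SAEs (Trial Summary, 2.2.2), where these routes matter most. All of this stands, and it confines the problem to the two exposed categories. It does not remove it, because objective (a) names adverse events without limiting them to serious ones.

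A second reply is that the choice of events for each harms table belongs to the SAP, and that section 7.2 fixes no harms test. That is fair, and no wrong analysis is alleged. But the unequal ascertainment is set by the protocol, and an SAP can correct for it only if the source of each event is known.

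A third reply is that an assessor-only comparison has its own weakness. Recall may be poor, participants may not repeat what they have already told the delivery team, and a 48-hour look-back would miss the exercise period. This also stands, so the fix must settle the look-back. Weekly enquiry during remote exercise is a safety feature, and nothing here argues against it.

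**Conclusion.** The point holds in a limited form and should be addressed. As written, the plan gives unequal ascertainment of non-serious AEs outside Table 4 and of SAEs known only by patient report, and the likely direction is over-counting in the intervention arm relative to control. The count of up to seven enquiries against one comes from the protocol. The risk ratios of 1.29 to 1.80 and the false-significance figures rest wholly on assumed detection rates and are not estimates for this trial.

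A reader might infer more than the document supports:

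- That the whole harms comparison is biased. Deaths, readmissions and Table 4 events reach the data by routes common to both arms.
- That all recorded events will be pooled regardless of source. Section 5.1.1 already separates Table 4 events, and section 7.2 does not define a pooled table.
- That the source of events is not captured. The eCRF is not shown, and 5.1.1 and 5.2.1 name distinct reporters, so it may be.
- That control events are found only at scheduled assessments. This is true of active enquiry, not of site reports.

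**What to change.** 1. Keep the weekly safety enquiry in the intervention arm unchanged.
2. Record the source of each AE and SAE (weekly session, assessor, site) on the eCRF, if it is not already captured.
3. State that the between-arm comparison for objective (a), and the comparative DMC tables, use sources common to both arms: the assessor's enquiry at week 8 and month 6, plus site-reported readmissions and deaths.
4. State in 5.2.1 that the week-8 assessor asks both arms about the whole period since randomisation, including events already reported at sessions, and reconcile this with the 48-hour wording.
5. Report session-only events separately, descriptively, for the intervention arm.

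The cost is at most one eCRF field, a clarified sentence in 5.2.1, an assessor prompt and matching SAP text. Session-only events leave the comparative table, though they are still reported. Recall of weeks 1-6 will be incomplete in both arms, and some difference may remain because weekly questioning can affect what participants later remember or repeat. The change removes the main distortion but does not make ascertainment identical.

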5.2.2 Related SAEs

Any SAEs that are assessed as related to the intervention will be reported according to the WCTU protocol.

5.2.3 Expected SAEs

There are no expected serious adverse events previously documented for this intervention. Therefore, any that are assessed as having a causal relationship to the intervention will not undergo expectedness assessment and will automatically be expedited to the REC as per section 5.2.4 below.

5.2.4 Reporting SAEs

The trial management team at WCTU will liaise with the intervention team/outcome assessor/investigator site to compile all the necessary information. Once the SAE form has been completed, causality will be independently assessed by the Chief Investigator (or delegate). SAEs that are deemed to be possibly, probably or definitely related to the trial interventions or outcomes assessments (by either the intervention team/outcome assessor/investigator site or the CI), will be notified to the Research Ethics Committee (REC) and sponsor within 15 days. All such events will be reported to the TMG, Sponsor, Trial Steering Committee and Data Monitoring Committee at their next meetings. All other recruiting sites in the trial must also be informed of the event and any implications for the trial.

5.2.5 SAE Follow-up

Any change of condition or other follow-up information should be sent to WCTU QA Team as soon as it is available or at least within 24 hours of the information becoming available. A member of the PI's trial team will be instructed to closely monitor each participant who experiences a SAE, until the outcome of the SAE has been determined. All participants experiencing SAEs will be followed-up until the event has been resolved or a final outcome has been reached as per protocol until the end of the trial.

5.2.6 Annual reporting

All SAEs will be recorded for inclusion in annual reports to the Research Ethics Committee.

5.3 Safety

If an AE/SAE occurs during the assessment or intervention, the person responsible for the patient should decide whether it is safe to continue the assessment/intervention, with or without modification, or whether it should be discontinued. SAEs will be reviewed/monitored by the TMG for trends.

The instructions for remote/home exercise will include appropriate warnings regarding when to stop exercise, e.g., chest pain, faintness, and dizziness, and a contact telephone number for the trial team. Participants will also be advised to follow usual procedures for any medical emergencies.

5.4 Responsibilities

Independent assessor/Intervention delivery team:

1. Checking for AEs/SAEs during participant assessments and treatment.
2. Ensuring that all AEs are recorded on the AE log and using clinical judgement in assigning seriousness and causality to AEs as applicable.
3. Ensuring that all SAEs are reported to Warwick CTU within 24 hours of becoming aware of the event and providing any additional information as appropriate.

Principal Investigator:

1. Using clinical judgement in assigning seriousness & causality to SAEs.
2. Ensuring that all SAEs received from WCTU are reviewed and appropriately reported back within 2 working days of receipt and providing further follow-up information as soon as available.
3. Ensuring that SAEs are recorded and reported to Warwick in line with the requirements of the protocol.

Chief Investigator / delegate or independent clinical reviewer:

1. Clinical oversight of the safety of patients participating in the trial, including an ongoing review of the risk / benefit.
2. Using clinical judgement in assigning seriousness & causality of SAEs where it has not been possible to obtain local medical assessment.
3. Immediate review of all related SAEs
4. Review specific SAEs in accordance with the trial risk assessment and protocol as detailed in the Trial Monitoring Plan.
5. Production and submission of annual reports to the relevant REC.

Sponsor (or delegate):

1. Oversight of safety reporting process, review of cumulative safety data
2. Reporting safety information to the CI, delegate, or independent clinical reviewer for the ongoing assessment of the risk / benefit according to the Trial Monitoring Plan.
3. Reporting safety information to the independent oversight committees identified for the trial (DMC and TSC) according to the Trial Monitoring Plan.
4. Expedited reporting of related SAEs to the REC within required timelines.
5. Notifying Investigators of related SAEs that occur within the trial.

Trial Steering Committee:

In accordance with the Trial Terms of Reference and/or charter for the TSC, periodically reviewing safety data and liaising with the DMC regarding safety issues.

Data Monitoring Committee:

In accordance with the Trial Terms of Reference and/or charter for the DMC, periodically reviewing unblinded overall safety data to determine patterns and trends of events, or to identify safety issues, which would not be apparent on an individual case basis.

5.5 Hospital Readmissions

Investigator sites will be asked to report all hospital readmissions to the trial team via the eCRF. The trial team will use the date of the readmission to help determine, along with the investigator site, whether this constitutes an SAE.

5.6 Notification of deaths

All deaths will be reported to the sponsor (Ulster University) and WCTU irrespective of whether the death is related to disease progression, the intervention, or an unrelated event. These should be reported within 24 hours of a staff member becoming aware of the event to WCTU using the eCRF.

5.7 Reporting urgent safety measures

If any urgent safety measures are taken, the trial management team at Warwick CTU as delegated by the CI/Sponsor shall immediately and, in any event, no later than 3 days from the date the measures are taken, give written notice to the relevant REC of the measures taken and the circumstances giving rise to those measures.

6. DATA MANAGEMENT

Personal data collected during the trial will be handled and stored in accordance with the UK General Data Protection Regulation and Common law Duty of Confidentiality.

Personal identifying information and Confidential Patient Information will be collected via the WCTU online database. Participants' details will be stored and accessed by staff at WCTU, Ulster University, Belfast HSCT and The Queens University Belfast via the online database to contact the participants during the trial, allow postage of participant materials, enable delivery of the intervention and to conduct the qualitative interviews. Handling of personal and confidential data will be clearly documented in the participant information sheet and consent obtained.

The iRehab intervention delivery team at Ulster University and Belfast HSCT will also keep records of participant contact details and medical health information for those participants randomised to the iRehab intervention. This is required for trial delivery to ensure participants are exercising at the appropriate level and to be used if a medical emergency occurs. These records will be stored securely and will not be passed on to anyone outside of the intervention delivery team.

Disclosure of confidential information will only be considered if there is an issue which may jeopardise the safety of the participant or another person, according to Warwick SOPs (Warwick SOP 15 part 1) and the UK regulatory framework. There is no reason to expect this situation to occur in this trial more than any other.

6.1 Data collection and management

Trial CRFs and participant questionnaires will be developed to collect all trial data. These CRFs will be developed by the WCTU trial management team in consultation with the CI, statistician, health economist and other relevant members of the trial team.

We will use the standard WCTU web-based application for trial management to record participant data in accordance with the trial protocol. The CRFs will be developed by WCTU team and made available to the participating sites as either paper or electronic CRFs (eCRFs) for ease of data collection; supporting materials will also be available to staff. All documents will be stored safely with restricted access to maintain confidentiality. On all trial-specific documents, other than the consent form, the participant will be referred to by a unique trial-specific number/patient identifier/code in any database, not by name. The trial will be conducted in accordance with the current approved protocol, Good Clinical Practice (GCP), relevant data protection regulations and standard operating procedures (SOPs). A monitoring plan and risk assessment will be devised to protect participant safety

and integrity of trial data. Routine monitoring procedures will be conducted the frequency of which will be determined by each sites rate of recruitment and safety of permitting staff to conduct visits.

Various methods will be used to track missing data including phone, text, and email. Participants will receive a reminder to complete the online questionnaires at each time point alongside a video/telephone call from the independent assessor at WCTU. If a participant has not completed a questionnaire at the follow-up assessment timepoint the independent assessor will encourage them to complete the questionnaire online or provide support for this to be completed via phone (using the reference copy of the questionnaires previously provided). If data remain missing, the independent assessor will make further contact with the participant to attempt to collect the outcome measurements with priority for the core measures.

Data will still be collected for participants who discontinue or deviate from the protocol, unless they withdraw their consent (section 2.1.2). For any participants who do not respond to the follow-up assessment calls or who are known to have died, WCTU will request a death notification form be completed by the recruiting hospital site.

Identifiable data that we no longer require or information that could identify anyone by name will be deleted 12 months after trial completion (last follow-up for last participant). We will have to keep non-identifiable (pseudonymised) data for up to 10 years.

6.2 Database

The iRehab database will be developed by the Programming Team at WCTU and all specifications (i.e. database variables, validation checks, screens) will be agreed between the programmer and appropriate trial staff.

